8.3.3. Vital Signs and Temperature Monitoring

Vitals will include blood pressure, pulse, respiratory rate, and body temperature. Blood pressure and pulse will be taken with the participant in the recumbent, semirecumbent, or sitting position after 5 minutes of rest. Abnormal vital sign results identified after the first dose of study treatment constitute an AE if they are considered clinically meaningful, induce clinical signs or symptoms, require concomitant therapy, or require changes in itacitinib.

Temperature should be monitored starting on Day -3 through EOT (Day 28 ± 2 days). Any temperature $\geq 38^{\circ}\text{C}$ should be documented for CRS grading.

The participant will be encouraged to use a TempTraq® device as a tool for temperature monitoring. Additional instructions regarding the TempTraq device will be provided separately. If a participant is unable to wear the device at any point during the treatment period, this will not be considered a Protocol deviation.

8.3.4. Eastern Cooperative Oncology Group Performance Status

The ECOG performance status will be assessed as indicated in [Table 3](#) according to the criteria in [Table 14](#).

Table 14: Eastern Cooperative Oncology Group Performance Status Scoring

Grade	Performance Status
0	Fully active, able to carry on all predisease performance without restriction.
1	Restricted in physically strenuous activity but ambulatory and able to carry out work of a light or sedentary nature, eg, light house work, office work.
2	Ambulatory and capable of all self-care but unable to carry out any work activities. Up and about more than 50% of waking hours.
3	Capable of only limited self-care, confined to bed or chair more than 50% of waking hours.
4	Completely disabled. Cannot carry on any self-care. Totally confined to bed or chair.
5	Dead.

Source: [Oken et al 1982](#).

8.3.5. Local Laboratory Assessments

See [Table 15](#) for the list of clinical laboratory tests to be performed and the SoA (see [Table 3](#)) for the timing and frequency. A certified laboratory local to the investigative site will perform all clinical laboratory assessments except as identified in [Table 16](#) and [Table 17](#).

The investigative site will enter the laboratory results and laboratory normal ranges into the eCRF. Additional testing may be required by the sponsor based on emerging safety data. Additional tests may also be performed if clinically indicated.

Clinically significant abnormal laboratory findings are those that are not associated with the underlying disease, unless judged by the investigator to be more severe than expected for the participant's condition. All laboratory tests with values considered clinically significantly abnormal during participation in the study or within 30 days after the last dose of itacitinib should be repeated until the values return to normal or baseline or are no longer considered clinically significant by the investigator or medical monitor. See [Appendix D](#) for management of potential Hy's Law cases.

Screening laboratory assessments must be performed within 7 days of Day -3. If performed more than 3 days before Day -3, then the tests must be repeated and eligibility confirmed before study treatment administration on Day -3. Laboratory samples collected on study Day -3 must be performed before study treatment administration.

Table 15: Required Laboratory Analytes

Chemistry	Hematology	Urinalysis With Microscopic Examination	Serology	Coagulation
Albumin	Complete blood count, including:	Color and appearance	Hepatitis B surface antigen	PT
Alkaline phosphatase	Hemoglobin	pH and specific gravity	Hepatitis B surface antigen antibody	PTT or aPTT
ALT	Hematocrit	Bilirubin	Hepatitis B core antibody	INR
AST	Platelet count	Glucose	HBV-DNA	
Amylase	Red blood cell count	Ketones	HCV antibody	
Bicarbonate or CO ₂	White blood cell count	Leukocytes	HCV-RNA	
Blood urea nitrogen or urea	Differential count, including:	Nitrite		
Calcium	Basophils	Occult blood		
Chloride	Eosinophils	Protein		
Creatinine	Lymphocytes			
Glucose	Monocytes			
Lactate dehydrogenase	Neutrophils			
Lipase	Absolute values must be provided for:			
Phosphate				
Potassium				
Sodium				
Total bilirubin				
Direct bilirubin (if total bilirubin is elevated above ULN)				
Total protein				
Uric acid				
			Lipid Panel	Ferritin Level
			Total cholesterol Triglycerides LDL HDL	Ferritin level
				C-Reactive Protein
				CRP

aPTT = (activated) partial thromboplastin time; HDL = high-density lipoprotein; INR = international normalized ratio;

LDL = low-density lipoprotein; PT = prothrombin time

Note: Additional tests may be required, as agreed upon by the investigator and sponsor, based on emerging safety data.

8.3.5.1. Pregnancy Testing

A serum pregnancy test will be required for all women of childbearing potential during screening, the Day 28 visit, and the 30-day follow-up visit. A urine or serum pregnancy test may be collected on Day -3 before administration of itacitinib. If the participant is going to hospice, the Day 28 pregnancy test may be omitted. Additionally, urine pregnancy tests should be performed as medically indicated (eg, in case of loss of menstrual cycle, when pregnancy is suspected). If a urine pregnancy test is positive, the results should be confirmed with a serum pregnancy test.

If the serum pregnancy test is negative after a urine test was positive, the investigator will assess the potential benefit/risk to the participant and determine whether it is in the participant's best interest to resume itacitinib and continue participation in the study.

If a pregnancy is confirmed by a serum pregnancy test, see Section 9.7 for reporting requirements.

8.3.5.2. Serology

If hepatitis status is obtained within 60 days of the screening visit, that result may be used for this study. HBV/HCV testing should be repeated if there is any clinical suspicion of active hepatitis during screening. If hepatitis status is not known, hepatitis screening assessments will be performed at the screening visit to rule out hepatitis infection; required analytes are shown in [Table 15](#). Generally, hepatitis tests should be performed early in the screening process due to the length of time needed to obtain the results. Additional tests may be performed if clinically indicated. Hepatitis PCR assays only required if serology is positive. HBV-DNA does not need to be performed if the anti-HBs is the only positive result (indicating immunity due to vaccination).

The eligibility of any participant with positive viremia (eg, PCR assay targets detected) must be discussed with the medical monitor before participant enrollment.

[figure not shown]
8.4. Hematologic Disease Status

Participants are expected to have an objective assessment of disease status using PET/CT/MRI or bone marrow biopsy according to the institution's standard of care and the participant's hematologic disease. The results of these assessments will be recorded in the eCRF at screening, Day 28, restaging of disease, and at post-treatment follow-up visits (90 days and 180 days post-IEC treatment). If a disease assessment occurs at a different timepoint, per institutional guidelines, then this is acceptable. Any hematologic disease assessments that are conducted during the study should be captured in the eCRF.

A bone marrow assessment performed within 180 days of Day -3 can be used for the purpose of this study.

Additional information with regard to response criteria that should be used for lymphoma is provided in [Appendix E](#).

Additional information with regard to response criteria that should be used for ALL is provided in [Appendix F](#).

8.7. Unscheduled Visits

Unscheduled study visits may occur at any time during the study if medically warranted. Data from all assessments performed at unscheduled visits must be recorded in the eCRF.

8.8. End of Treatment

Per the Protocol, Day 26 is the last expected day of study treatment administration. An EOT visit will be conducted at Day 28 (\pm 2 days).

If the participant discontinues study treatment before Day 26, the EOT visit will still be conducted.

Unless the participant withdraws consent, all study assessments should continue to be performed and captured in the eCRF.

8.9. Follow-Up

8.9.1. Safety Follow-Up

The safety follow-up period is the interval between the last dose of study treatment and the scheduled safety follow-up visit, which will occur approximately 30 days after the last dose of itacitinib. Adverse events and SAEs must be reported up until 1) at least 30 days after the last dose of study treatment or 2) until toxicities resolve, return to baseline, or are deemed irreversible, whichever is longer. Reasonable efforts should be made to have the participant return for the 30-day safety follow-up visit and report any AEs that may occur during this period. If the participant cannot return to the site for the 30-day safety follow-up visit (eg, lives far away), the participant should be contacted by telephone for assessment of AEs and SAEs. This contact should be documented in the source and eCRF.

8.9.2. Hematologic Disease Follow-Up

All participants are expected to be followed, and hematologic disease status should be collected, until EOS (Day 180), unless informed consent is withdrawn.

During the follow-up period, hematologic disease assessments should be conducted at Day 28, restaging of disease, Day 90, and Day 180. However, if disease assessments are performed at different timepoints, based on institutional guidelines, then this is acceptable. All disease assessments should be captured in the eCRF. For additional guidance, see Section [8.4](#), [Appendix E](#), and [Appendix F](#).

8.9.3. Electrocardiograms and Echocardiograms

A 12-lead ECG will be obtained as outlined in the SoA (see [Table 3](#)) using an ECG machine that automatically calculates the heart rate and measures PR, QRS, QT, and QTc intervals. All 12-lead ECGs will be performed with the participant in a recumbent or semirecumbent position after 5 minutes of rest.

The 12-lead ECGs will be interpreted by the investigator at the site to be used for immediate participant management. Additional 12-lead ECGs may be performed as clinically indicated to manage participant safety.

The decision to include or exclude a participant or withdraw a participant from the study treatment based on an ECG flagged as "Abnormal, Clinically Significant" is the responsibility of the investigator, in consultation with the sponsor's medical monitor, as appropriate. Clinically notable abnormalities that are considered clinically significant in the judgment of the investigator are to be reported as AEs.

An assessment of LVEF will be performed locally by ECHO or multigated analysis to determine the cardiac function of the participant and to confirm study eligibility. If cardiac functional status is obtained within 60 days of the screening visit, for the purposes of IEC therapy, that result may be used for this study.

8.9.4. Survival Follow-Up

Participants will be contacted by telephone, email, or with a visit to assess for survival. All participants will be followed for survival until EOS (Day 180), unless informed consent is withdrawn.

8.10. End of Study

End of study is defined as participants who complete Day 180 or who withdraw their informed consent.

The EOS will be recorded in the eCRF and will mark the end of the study for the participant.

9. ADVERSE EVENTS: DEFINITIONS AND PROCEDURES FOR RECORDING, EVALUATING, FOLLOW-UP, AND REPORTING

9.1. Definition of Adverse Event

Adverse Event Definition

• An AE is any untoward medical occurrence associated with the use of a drug in humans, whether or not considered drug-related.• An AE can therefore be any unfavorable and unintended sign (including an abnormal laboratory finding), symptom, or disease (new or exacerbated) temporally associated with the use of study treatment.
Events Meeting the Adverse Event Definition

• Any safety assessments (eg, ECG, vital signs measurements), including those that worsen from baseline (Day -3), considered clinically significant in the medical and scientific judgment of the investigator (ie, not related to progression of underlying disease).• Abnormal laboratory test results constitute an AE if they are considered clinically meaningful, induce clinical signs or symptoms, require concomitant therapy, or require changes in study treatment. Whenever possible, a diagnosis (eg, anemia, thrombocytopenia) should be recorded in the eCRF rather than the abnormal lab result (eg, low hemoglobin, platelet count decreased).• Exacerbation of a chronic or intermittent pre-existing condition including either an increase in frequency and/or intensity of the condition.• New conditions detected or diagnosed after study treatment administration even though they may have been present before the start of the study.• Signs, symptoms, or the clinical sequelae of a suspected drug-drug interaction.• Signs, symptoms, or the clinical sequelae of a suspected overdose of either study treatment or a concomitant medication. Overdose per se will not be reported as an AE/SAE unless it is an intentional overdose taken with possible suicidal/self-harming intent. Such overdoses should be reported regardless of sequelae.• "Lack of efficacy" or "failure of expected pharmacological action" per se will not be reported as an AE or SAE. Such instances will be captured in the efficacy assessments. However, the signs, symptoms, and/or clinical sequelae resulting from lack of efficacy will be reported as an AE or SAE if they fulfill the definition of an AE or SAE. As an example, CRS or neurotoxicities will not be recorded as lack of efficacy but will be recorded as AEs/SAEs as appropriate.
Events NOT Meeting the Adverse Event Definition

• Any clinically significant abnormal laboratory findings or other abnormal safety assessments that are associated with the underlying disease, unless judged by the investigator to be more severe than expected for the participant's condition.• The disease/disorder being studied or expected progression, signs, or symptoms of the disease/disorder being studied, unless more severe than expected for the participant's condition or considered to be treatment-related by the investigator.• Efficacy endpoints as outlined in Section 3 will not be reported as AE/SAEs, specifically, any event that is related to disease progression of the cancer under study. Unblinded aggregated efficacy endpoint events and safety data will be monitored to ensure the safety of the participants in the study. Any suspected endpoint that upon review is not progression of the cancer under study will be forwarded to Incyte Pharmacovigilance as a SAE within 24 hours of determination that the event is not progression of the cancer under study.

- Medical or surgical procedure (eg, endoscopy, appendectomy): the condition that leads to the procedure is the AE if it occurred after signing informed consent. If present before entering the study, the condition should be captured as medical history.
- Situations in which an untoward medical occurrence did not occur (social and/or convenience admission to a hospital).
- Anticipated day-to-day fluctuations of pre-existing disease(s) or condition(s) present or detected at the start of the study that do not worsen.

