3. OBJECTIVES AND ENDPOINTS

Table 7 presents the objectives and endpoints for Part 1 and Part 2, supporting selection of optimal dosing/schedule of itacitinib for subsequent trials.

Table 7: Objectives and Endpoints

Objectives	Endpoints
Primary	
To evaluate the efficacy of itacitinib as a preventative treatment for CRS associated with IEC therapy.	Efficacy, as determined by the proportion of participants who develop \geq Grade 2 CRS by Day 14, using ASBMT CRS Consensus Grading.
Secondary	
To evaluate the proportion of participants with ICANS regardless of CRS, after IEC therapy.	Incidence and severity of ICANS, as determined by the proportion of participants with ICANS by Day 28, after IEC therapy using the ICANS Consensus Grading.
To evaluate the onset and episode of ICANS using the ICANS Consensus Grading, regardless of CRS, by Day 28.	Time to onset and duration of ICANS using the ICANS Consensus Grading, regardless of CRS, by Day 28.
To evaluate the duration of all grades of CRS, by Day 28.	Time to onset and duration of all grades of CRS by Day 28 using ASBMT CRS Consensus Grading.
To evaluate the proportion of participants who develop any grade of CRS within 48 hours after IEC therapy.	Proportion of participants with any grade of CRS at 48 hours, after IEC therapy using ASBMT CRS Consensus Grading.
To evaluate the proportion of participants who develop \geq Grade 2 CRS by Day 28 of administration after first IEC therapy.	Proportion of participants with \geq Grade 2 CRS by Day 28, after first IEC therapy.
To characterize the safety of itacitinib, before and after IEC therapy, excluding CRS and ICANS.	Safety of itacitinib assessed by the incidence of all AEs except CRS and ICANS, by collecting laboratory data, performing physical examinations, and collecting vital signs beginning at Day -3 and through the duration of safety follow-up.
	\geq Grade 3 Cytopenias ongoing by Day 30.
To evaluate the number of and length of hospital admissions for CRS and ICANS.	Number of hospital admissions and duration of stay for participants with CRS and/or ICANS by EOS.
To assess intervention for CRS and ICANS.	Proportion of participants who were treated with tocolizumab for CRS.
	Proportion of participants requiring more than 1 dose of dexamethasone (or equivalent) for ICANS.

Table 7: Objectives and Endpoints (Continued)

Objectives and Endpoints	Definition

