9.2. Definition of Serious Adverse Event

If an event is not an AE per definition above, then it cannot be an SAE even if serious conditions are met (eg, hospitalization for signs/symptoms of the disease under study, death due to progression of disease).

A Serious Adverse Event is defined as any untoward medical occurrence that, at any dose:

a. Results in death

b. Is life-threatening

The term 'life-threatening' in the definition of 'serious' refers to an adverse drug experience that places the participant, in the opinion of the initial reporter, at immediate risk of death from the adverse experience as it occurred. This does not include an adverse drug experience that, had it occurred in a more severe form, might have caused death.

c. Requires inpatient hospitalization or prolongation of existing hospitalization

In general, hospitalization signifies that the participant has been detained (usually involving at least an overnight stay) at the hospital or emergency ward for observation and/or treatment that would not have been appropriate in the physician's office or outpatient setting. Complications that occur during hospitalization are AEs. If a complication prolongs hospitalization or fulfills any other serious criteria, the event is serious. When in doubt as to whether "hospitalization" occurred or was necessary, the AE should be considered serious.

Hospitalization for elective treatment or planned surgery (eg, stent replacement, hip surgery) is not considered an SAE.

Hospitalization for medical interventions in which no unfavorable medical occurrence occurred (ie, elective procedures or routine medical visits) is not considered an SAE.

d. Results in persistent or significant disability/incapacity

- The term disability means a substantial disruption of a person's ability to conduct normal life functions.
- This definition is not intended to include experiences of relatively minor medical significance, such as uncomplicated headache, nausea, vomiting, diarrhea, influenza, and accidental trauma (eg, sprained ankle), that may interfere with or prevent everyday life functions but do not constitute a substantial disruption.

e. Is a congenital anomaly/birth defect

f. Other situations (Important Medical Event)

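### Protocol 9.1 ties its AE/SAE exclusion to the Section 3 efficacy endpoints, which are CRS and ICANS rather than cancer progression, and its forwarding sentence, read literally, makes every CRS or ICANS event an SAE

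*Protocol*

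**What the plan says.** Protocol 9.1 gives three instructions that bear on CRS and ICANS.

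- Under events that do not meet the AE definition: "Efficacy endpoints as outlined in Section 3 will not be reported as AE/SAEs, specifically, any event that is related to disease progression". The sentence goes on to name the cancer under study.
- Later in the same bullet: "Any suspected endpoint that upon review is not progression of the cancer under study will be forwarded to Incyte Pharmacovigilance as a SAE". The time limit given is 24 hours from the determination that the event is not progression.
- Under events that do meet the definition, as an illustration of the lack-of-efficacy rule: "CRS or neurotoxicities will not be recorded as lack of efficacy but will be recorded as AEs/SAEs as appropriate".

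Protocol 9.2 then makes the AE definition a gate for seriousness: "If an event is not an AE per definition above, then it cannot be an SAE even if serious conditions are met". Protocol 9.4 sets the general SAE clock at 24 hours from learning of the event, subject to anything the Protocol specifies otherwise.

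In Section 3 (Table 7) the primary objective reads "To evaluate the efficacy of itacitinib as a preventative treatment for CRS associated with IEC therapy". Its endpoint begins "Efficacy, as determined by the proportion of participants who develop" and concerns Grade 2 or higher CRS by Day 14. The first secondary endpoint is "Incidence and severity of ICANS, as determined by the proportion of participants with ICANS by Day 28". The safety endpoint is "Safety of itacitinib assessed by the incidence of all AEs except CRS and ICANS", supported by laboratory, examination and vital-sign data.

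**The concern.** The exclusion points to Section 3 for its list of endpoints and then describes them as progression events. In the legible part of Table 7 no endpoint is progression. The events a site finds there are the ones that another part of 9.1 tells it to record as AEs or SAEs. The forwarding sentence compounds this: CRS is a study endpoint and is never cancer progression, so on its words it is always forwarded as an SAE.

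Two things depend on how sites resolve this. The first is expedited reporting of serious CRS and ICANS, including when the 24 hours start. The overall-design text after Table 7 keeps the sponsor unblinded in Part 2 so that it can monitor the safety of the BID cohort. The second is the set of tables in SAP 9.2.2, which count participants with any serious TEAE by treatment group and list serious TEAEs by term. SAP 9.2.2 states no exclusion for CRS or ICANS. If sites differ in what they report, those tables mix reporting practice with event frequency.

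**Working it through.** No figure in the plan is at issue, so the check is a comparison of the texts.

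**Step 1. Do the Section 3 endpoints match the exclusion?** The efficacy endpoints legible in Table 7 are Grade 2 or higher CRS by Day 14 and by Day 28, any CRS at 48 hours, onset and duration of CRS, and incidence, severity, onset and duration of ICANS. Hospital stays and rescue use related to CRS and ICANS are also listed. None is progression. The remaining endpoints concern AEs and cytopenias. The reference to Section 3 and the description that follows it therefore name different events.

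**Step 2. Does the limiting word settle the first sentence?** Largely. *Specifically* narrows the exclusion to progression. Three other texts agree that CRS and ICANS are AEs: the lack-of-efficacy bullet in 9.1, the intensity rules in 9.3 (which grade CRS and ICANS events on the ASBMT scales), and the safety endpoint in Table 7, which excludes CRS and ICANS from the AEs and so presupposes that they are AEs.

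**Step 3. Does it settle the forwarding sentence?** No. That sentence covers any suspected endpoint that is not progression, states no seriousness test, and starts its own clock. Narrowing the first sentence does not narrow this one.

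**Step 4. What does each sentence give if a site follows it literally?**

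| Sentence followed | Non-serious CRS (e.g. Grade 1, fever only) | Serious CRS |
|---|---|---|
| 9.1 exclusion, read by its Section 3 reference | Not an AE | Not an AE, so barred from SAE status by 9.2 |
| 9.1 lack-of-efficacy bullet, with 9.2 and 9.4 | AE | SAE, 24 hours from learning of the event |
| 9.1 forwarding sentence | SAE | SAE, 24 hours from determining it is not progression |

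Non-serious CRS has three possible classifications. Serious CRS has two, unreported or SAE, with two clocks for the second. ICANS behaves in the same way.

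**Step 5. Which clock prevails?** The reservation in 9.4 for other Protocol rules allows the 9.1 clock to be read as the exception, so 9.4 does not resolve the difference by itself.

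**The case against.** The strongest reply is that, read in context, 9.1 already works. The exclusion is limited by its own words to progression. The only sentence in 9.1 that names CRS and neurotoxicity says they are recorded as AEs or SAEs. The bar in 9.2 applies only to non-AEs, and its examples are the disease under study and its progression. The forwarding sentence follows directly on the progression exclusion, so it can be taken to cover events first withheld as suspected progression and later found to be something else. A post-infusion fever graded as CRS is never withheld in that way, and on this reading the two clocks apply to different events.

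Most of this stands. It is the more natural reading, and a reader who inferred that the Protocol tells sites not to report serious CRS would go too far. It does not remove the point. The contextual limit on the forwarding sentence is not in its wording, and the Section 3 reference remains wrong for the events it is meant to describe.

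Two further objections also stand. Amendment 3 refers to an exploratory tier that is not legible in Table 7, and the SAP lists response assessments among its efficacy listings, so Section 3 may contain a disease-response endpoint in removed text. That would explain the reference, but CRS and ICANS would still be Section 3 endpoints. Monitoring also does not rest on SAE reports alone: CRS and ICANS have their own eCRF forms (Protocol 8.2.1 and 8.2.2), are evaluated at each visit, and 9.1 provides for unblinded monitoring of aggregated endpoint and safety data.

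**Conclusion.** The concern holds as an inconsistency in operative safety-reporting text. It is worth correcting because the correction is cheap and concerns the events the trial studies. It is not evidence that serious CRS will go unreported, or that every CRS will become an SAE; those are the two literal extremes.

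No numerical size is established. A reader might be tempted to use the Part 2 planning rates of 50% and 20% with 23 per arm: 23 × 0.50 + 23 × 0.20 = 11.5 + 4.6 = 16.1 of 46, or 35%, with Grade 2 or higher CRS, and a 30-point gap between arms. The documents do not support either figure as an estimate of misreporting. Some of those events would meet a seriousness criterion under any reading. The SAP counts participants with any serious TEAE, so some would be counted for another event. No arm-specific rates are assumed for Grade 1 CRS or for ICANS. The 30 points are simply the assumed treatment effect.

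The primary endpoint is protected because CRS grade is captured on the dedicated form. What is exposed is the consistency and timing of SAE reports, and the serious-TEAE tables by arm. The effect on the tables assumes that they include CRS and ICANS, as SAP 9.2.2 implies by stating no exclusion.

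**What to change.** Reconcile the passages in Protocol 9.1 with three changes.

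1. Limit the exclusion to progression of the underlying malignancy and remove the reference to Section 3.
2. State that CRS and ICANS follow the ordinary AE/SAE rules: always AEs, SAEs when a 9.2 criterion is met, reported on the 9.4 clock.
3. Confine the forwarding sentence to events first withheld as suspected progression and later found not to be progression.

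The cost is a few sentences in an amendment and a letter to sites, and possibly a few more SAE forms where a site had relied on the exclusion. The design, endpoints and sample size do not change.
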